12.0 Follow-up - NA

13.0 Genetic Analysis Information - NA

14.0 Sharing of Results with Subjects - NA

15.0 Risks to Subjects

15.1 List the research risks. Research risks are any potential physical, psychological, social, legal, privacy, confidentiality risks or economic harms that may come from participating in the study. This does not include the risk of any procedures conducted as part of standard care.

There is a slight risk of skin irritation from the actigraph and actiwatches. Because the research requires the collection of PHI, there is a risk breach of confidentiality. There is a small chance that disclosing this information may potentially lead to emotional discomfort for some families. There also is a risk to confidentiality when using the internet. Pregnant women may participate as there is no risk beyond that of PA within healthy guidelines. No additional costs are associated with this study, except the potential of a participant to exceed data allowances for their plan with their cell phone carrier.

If the devices cause more than minimal discomfort, participants will be instructed to notify the study team. Minimizing risk of confidentiality is described in section 9.0. Regarding questions that may cause emotional discomfort, participants will be instructed that they may decline to answer any question that they do not feel comfortable answering. Participants will be informed any fees from their cell phone carrier incurred by exceeding their data plan limit will not be covered by the study. PA goals for participants that are pregnant will be set in collaboration with the participant and limited to healthy guidelines.

15.2 Indicate whether the researchers believe the risks involved in this study are minimal, or if the study poses greater than minimal risk of harm to subjects.

The overall risks of participation in this project are no more than minimal.

- **15.3** If applicable, indicate which procedures may have risks to the subjects that are currently unforeseeable. **NA**
- **15.4** If applicable, indicate which procedures may have risks to an embryo or fetus, should the subject be or become pregnant. **NA**
- **15.5** If applicable, describe risks to others who are not subjects (e.g. pregnant partner of a male subject) **NA**

16.0 Potential Benefits

16.1 Describe the potential of any direct benefits that individual subjects may experience from taking part in the research. Include the probability, magnitude, and duration of the potential benefits as this will be useful to the IRB in making their risk/benefit determination.

It is possible that some participants could improve their level of personal fitness and HbA1c level based on using the NUDGE intervention. There may not be direct benefit to being in this study, but by being in this study their child may help researchers find better treatments for people with T1D and how PA may help with managing T1D and other illnesses in the future.

16.2 Describe the potential of any benefits to society or others related to the possible knowledge gained.

NUDGE could benefit numerous populations in improving PA and subsequent health benefits that result from increased PA.

17.0 Investigator Assessment of Risk/Benefits Ratio:

17.1 Please provide an assessment of risk and benefits in the table below. Note, the IRB makes the final determination based upon responses in the two preceding sections.

Select as applicable:	Pediatric Risk Category:	
	Category 1	Research not involving greater than minimal risk (45 CFR §46.404 and 21 CFR
	Category 2	§50.51) Research involving greater than minimal risk but presenting the prospect of direct benefit to the individual subjects. (45 CFR §46.405 and 21 CFR §50.52)
	Category 3	Research involving greater than minimal risk and no prospect of direct benefit to individual subjects, but likely to yield generalizable knowledge about the subject's disorder or condition. (45 CFR §46.406 and 21 CFR §50.53)
	Category 4	Research not otherwise approvable which presents an opportunity to understand, prevent, or alleviate a serious problem affecting the health or welfare of children. (45 CFR §46.407 and 21 CFR §50.54)
Select if applicable:	Adult Risk Category:	850.51)
	Not Greater than Minimal Risk	
	Greater than Minimal Risk	
Will subjects receive payment, ⊠ Yes □ No (If No, or 18.1 Payment to S	reimbursement, or tangible Properties the following subsections) Subjects: If providing payment to time off work), select the form of payment to the payment to the form of payment to the form of payment to the payment to the for	o subjects (e.g. cash equivalent
☑ Greenphire/ClinCard/Rybbo☐ Gift Card: (Merchant:		

☐ Other:	

Payment Schedule:

Participants will receive up to \$648 of compensation for completion of the Study. See the Table below:

Initial Study Visit	Wearing Actiwatch		Completing Each EMA Surveys		I imely Device	Completing Treatment Satisfaction Survey	I otal Compensati
\$50	\$5/day (x21)	\$100	\$2 (\$168 possible)	\$100	\$75 (\$25 each)	\$50	\$648

To receive timely device return compensation, we ask that participants drop-off or schedule a package pick-up within a week after their wear week/visit finishes. Participants will have a simple two question survey to fill out the based on the date provided and receipt of the item within a reasonable/expected period for shipment, participants will qualify to receive compensation. Compensation will not be withheld from participants due to issues or delays caused by the mail carrier.

- **18.2** Subject Reimbursement: If providing reimbursement (repayment to research participants and/or their families to cover out-of-pocket expenses they incur), select the form of reimbursement: **NA**
- **18.3 Tangible Property:** If providing tangible property or any item of value given to research subjects for their participation (e.g. a toy, a tote bag, a water bottle, an electronic device), describe: **NA**

19.0 Compensation for Research-Related Injury – NA, Minimal Risk

20.0 Economic Burden to Subjects

20.1 Describe any costs that subjects may be responsible for because of participation in the research. This may include transportation to appointments, time away from work, parking, additional lab tests, et cetera.

The only costs participants may have from participating in this study could be from their cell phone carrier. They may charge participants message and data rates depending on their contract with their cell phone carrier. These charges, if any, will not be covered by this research study.

21.0 Permission/Assent/Consent Process

☑ Written informed permission of parent/LAR for pediatric participants

Study group(s) to which this method applies: Parent/LAR of pediatric participants

☑ Written informed consent of adult participants

Study group(s) to which this method applies: Adult participants (18 and above)

☑ Written informed consent of participants turning 18

Study group(s) to which this method applies: Participants who turn 18 while actively participating in study activities

☑ Waiver of consent of participants turning 18

Study group(s) to which this method applies: Participants who turn 18 and active participation has ended

21.1 Summarize the methods of permission/assent/consent that will be used for each study group. For example, "Full written permission and assent will be obtained for pediatric subjects in the experimental group. Verbal consent will be obtained from parents participating in the survey portion of the study. For the historical controls chart review group, we are applying for a waiver of parental permission and assent."

Informed consent will be obtained through e-consent via telephone or CM approved conferencing platform. Participants who turn 18 while actively participating in the study will be reconsented.

We request waiver of consent when patients turn 18 whose **active participation** has ended due to continued use of identifiable data. Unnecessary PHI will be destroyed upon completion of the study however, some PHI will need to be kept (date of enrollment, dates of visits, dates surveys completed) We cannot completely deidentify the data if we are unable to reach the subject.

This protocol, and any subsequent modifications, as well as patient-facing material will be reviewed and approved by the Pediatric IRB at The Children's Mercy Hospital & Clinics.

Regulatory Criteria: To qualify for a waiver or alteration of parental permission or adult consent, **ALL** of the following must apply. Explain how the study meets each of the regulatory criteria below.

Waiver of Consent when patients turn 18 whose active participation has ended:

Criteria	Explain how the study meets the criteria
The research involves no more	The research presents no more than minimal risk of harm to
than minimal risk to the	subjects and involves no procedures for which written permission
participants	is normally required outside of the research context.
The research could not	We request a wavier of consent when participants turn 18 and are
practicably be carried out without	no longer active in the study because we will need some PHI even
the requested waiver/alteration	after study procedures have been completed.
(i.e., explain why the study could	
not be done if	
permission/assent/consent were	
required)	

If the research involves using	We do include PHI as part of our dataset and will need to continue
identifiable private information or	to use even after participation has ended.
identifiable biospecimens, the	
research could not practicably be	
carried out without using such	
information or biospecimens in an	
identifiable format	
The waiver/alteration will not	The family will be made aware of this at enrollment. We will not
adversely affect the rights and	keep any PHI that is not necessary for the study.
welfare of the participants	
Whenever appropriate, the	Yes
participants or legally authorized	
representatives will be provided	
with additional pertinent	
information after participation	

Assent of Pediatric Participants

☑ Assent of pediatric participants WILL BE SOUGHT following assessment of ability to assent.

The study team will assess on a case-by-case basis, using best judgement and ensuring there were no notes in the medical record that indicates a participant would be unable to assent. Parents/LAR and participants will be made aware that participant assent is required upon initial contact. Study staff will ask to speak directly to the pediatric participant prior to the e-consent to answer any questions or concerns. The formal assent discussion will be conducted during the e-consent process and documented through REDCap. The length and content of the e-consent materials offer ample time and information for the participant to make any concerns or questions known and is designed to ensure participant comprehension.

22.0 HIPAA and Confidentiality

HIPAA regulations apply to this study if the data used or accessed relates to:

The past, present or future physical or mental health or condition of an individual;

The provision of health care to an individual; OR

The payment for the provision of health care.

22.1 HIPAA Authorization

Select all applicable methods of HIPAA Authorization that apply to this study. For each selection, click on the "" symbol to expand additional information required (if applicable).

☑ Full Written HIPAA Authorization will be obtained (within the p/a/c form or standalone form)

☑ Partial Waiver of HIPAA Authorization (e.g. waiver for recruitment and pre-screening purposes only)

☑ Other: Waiver of HIPAA Authorization at age 18 (authorization will NOT be obtained) for continued use of identifiable data from patients who turn 18 and active participation has ended.

Regulatory Criteria: To qualify for an alteration of HIPAA Authorization, **ALL** of the following must apply to your study. Explain how your study meets each of the regulatory criteria below.

Criteria	How your study meets the criteria
The use or disclosure of PHI involves no more than minimal risk to the privacy of individuals based upon the following: Plan to protect PHI from improper use and disclosure: Plan to destroy PHI at the earliest opportunity, unless there is a health or research justification for retaining the PHI: Assurance that PHI will not be reused or disclosed to any other person or entity:	We will protect PHI from improper use and disclosure as it will only be made available to study staff on an as-needed, IRB approved basis as noted in Section 5.0, Study Design, of this protocol. PHI will be destroyed after all publication has been completed. PHI will not be reused or disclosed to any other person or entity.
The research cannot practicably be conducted without the waiver, i.e. explain why you cannot obtain a signature for HIPAA Authorization.	Partial Waiver of HIPAA Authorization: Study staff will need to record information collected for the purposes of recruitment in the pre-screening log (e.g., eligibility met, clinic visits where study staff may approach families) as noted in Section 9.0, Screening and Recruitment Methods, of this protocol. Waiver of HIPAA Authorization at age 18: Permission/Assent will be obtained. The Waiver is limited to continued use of identifiable data from patients who turn 18 and active participation has ended.
The research cannot practicably be conducted without access to and use of the PHI, i.e. explain why you need the PHI to do this study.	Study staff will store PHI on non-participants until completion of enrollment. Study staff will do this to reduce the likelihood of reapproaching families who have already declined participation in the study as noted in Section 9.0, Screening and Recruitment Methods, of this protocol. All data collected is needed to meet the study aims.

22.2 *Indicate how the research team will protect the confidentiality of subjects' data during storage, use, and transmission. (e.g. training, authorization of access, password*

protection, encryption, physical controls, and separation of identifiers and data [master list]). Remember: Sensitive CM data, including research data, must be stored on a file server on the CM network domain – not on a workstation hard drive.

Information pertaining to protection of confidentiality of subject's data during storage, use, and transmission can be found in Sections 5.0 and 23.0 of this protocol.

22.3 State whether a Certificate of Confidentiality has been issued for this study. Certificates are automatically issued for NIH funded research per NIH policy. For non-federally funded research involving identifiable, sensitive information, investigators may apply for a Certificate if desired. See the NIH website on Certificates of Confidentiality for more details.

A Certificate of Confidentiality has not been issued for this study.

23.0 Provisions to Protect the Privacy Interests of Subjects

23.1 Describe the steps that will be taken to protect subjects' privacy during recruitment and while obtaining permission/assent/consent. For example, best practice is to obtain permission/assent/consent in a separate area where a private conversation can be had. If this is not possible, be sure to explain what steps will be taken to provide as much privacy as possible.

Participation in this research study is voluntary. Study staff will notify adult participants and the parents/LARs of youth of the voluntary status of the research at the onset of the study enrollment and receive informed permission/assent/consent during their e-consent study visit as explained in Section 5.0, Study Design, of this protocol and further explained in Section 9.0, Screening and Recruitment Methods, of this protocol. Any potential participant or parent/LAR who declines to participate will not incur any penalty or loss of benefits to which they are already entitled. No change to the participants' or parent's/LAR's medical care will occur as a result of the participation, or nonparticipation in the study.

Recruitment and consent may take place during a routine clinic visit in a private clinic room, over the phone, or over a CM approved conferencing platform.

23.2 Describe what steps you will take to make the subjects feel at ease with the research situation in terms of the questions being asked and the procedures being performed. "At ease" does not refer to physical discomfort, but the sense of intrusiveness a subject might experience in response to questions, examinations, and procedures.

Participants will be told that research is voluntary and that they do not have to answer any questions within the surveys that they do not want to answer.

23.3 *Indicate how the research team is permitted to access any sources of information about the subjects and how the research team will protect the confidentiality of subjects' data.*

Any of the research data collected, with the exception of PHI, may be shared in an aggregated form in presentations and publications. At the termination of the study, study staff will destroy the enrollment log and pre-screening log. During the course of the study, study staff will delete the PHI (with the exception of name and MRN) collected on potential subjects who do not wish to participate. Upon completion of the study, study staff will remove all unnecessary PHI in the data collection files and/or convert to a deidentified number. However, certain PHI will be kept: date of enrollment, dates of visits, and dates surveys were submitted.

NUDGE data is stored securely in two locations- the Twilio.com server and a secure server at the University of Kansas. Twilio uses an encryption protocol to protect the data in messages transferred between Twilio and the NUDGE Web application. NUDGE uses the TSL cryptographic protocol and HTTP authentication. These are the highest security levels available from Twilio at the time of the last software update for the NUDGE web app. Second, data are captured on a SQL Server instance behind a HIPAA compliant firewall in the Computing Center at the University of Kansas.

Study staff at Children's Mercy may access and record name, initials, dates of service, date of birth, medical record number, hospital account number, street address, fax number, telephone number, and email address for research purposes.

The University of Kansas team will have access to the participant's telephone number via the Nudge application. They will also have access to the participant addresses as part of PA tracking device shipment.

Research Team members will only access participant information per the methods approved by the IRB. CM approved lockboxes will be utilized to transport any documents containing PHI from one location to another and this will only be done when necessary. Electronic data will be stored and accessed per secure methods approved by the IRB.

Study staff will share as soon as it becomes available any new information gathered during the course of the study which might impact a family's desire to continue in the study.

24.0 Withdrawal of Subjects

24.1 *Describe the anticipated circumstances, under which subjects will be withdrawn from the research without their consent.*

The only foreseeable circumstances of withdrawal from the research without their consent would be subjects not meeting eligibility criteria.

24.2 *Describe any procedures for orderly termination.*

See Section 23.0, Provisions to Protect the Privacy Interests of Subjects, of this protocol for additional information and below in Section 24.3.

24.3 Describe procedures that will be followed when subjects withdraw from the research, including data retention plans or partial withdrawal from procedures with continued data collection.

Participants may withdraw from the study at any time, and this will not affect their medical care. Study staff will not collect any study-related data on participants after their withdrawal from the study. Data collected up to withdrawal will be included in the analyses, with the exception of those who are withdrawn from the study for not meeting eligibility criteria.

Also see Section 23.0, Provisions to Protect the Privacy Interests of Subjects, of this protocol.

DATA MANAGEMENT

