2.2 Hypotheses: *State the hypothesis to be tested.*

AIM 1: Test feasibility and initial efficacy of a novel mHealth intervention to promote PA in youth and YAs with T1D.

Hypothesis 1: Our application of a novel mHealth intervention to promote PA in youth and YAs with T1D will show feasibility based on ≥50% of daily text messages exchanged between youth and the intervention bot.

Hypothesis 2: Our application of a novel mHealth intervention to promote PA in youth and YAs with T1D will show initial efficacy based on the threshold of achieving at least a medium effect size for participant's daily PA.

AIM 2: Evaluate if increasing minutes of PA in youth and YAs with T1D promotes more optimal HbA1c levels.

Hypotheses 3: Youth and YAs with T1D who increase their daily PA based on our novel mHealth intervention will also show an improvement in their HbA1c levels.

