Study staff will provide youth and their parent/LAR and YA participants information about the study and answer any questions they may have in order to help them determine if they would like to participate as explained in Section 5.0, Study Design. Participants and parents/LARs of youth will have ample time to bring forward any questions or concerns during the period between recruitment contact and the e-consent process. Participants and parents/LARs will be presented with all study information during the e-consent process. At that time informed parental/LAR permission and/or participant assent/consent will be obtained. Study staff will take care to answer all questions and place no pressure on any potential participant or their parent/LAR to enroll.

To minimize risk, we will inform all participants, and parents/LARs of adolescent participants, that they do not have to participate and that a decision not to participate will not affect their care at CM. We will inform all participants and parents/LARs of adolescent participants of the risk of breach of confidentiality as well as these steps we will follow to reduce the risk of a breach of confidentiality and to protect their privacy (e.g., limiting access to data, de-identifying data, securing data in a secure CM network drive). We will inform participants that they can refuse to answer any question during the study. Similarly, we will inform participants that they can refuse to participate in any component of the study protocol and withdraw from the study at any time without penalty or loss of benefits.

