10.0 Procedures

10.1 Provide a description of research procedures of all research procedures being performed and when they are performed, including procedures being performed to monitor subjects for safety or minimize risks.

We will recruit eligible pediatric patients from the Pediatric Diabetes Clinic at Children's Mercy-Kansas City (CM) as explained in Section 9.0, Screening and Recruitment Methods of this protocol. We will use a tablet and/or computer and REDCap to collect family survey data, collect information from participant's Electronic Health Record (EHR) upon agreement to participate, and instruct participants in how to wear the actigraph and the actiwatch and track, and share data with the research team as explained in Section 5.0, Study Design of this protocol. Contact with participants via phone/email is explained in detail as well in Section 5.0. This study involves no more than minimal risk and procedures to minimize any potential risk to participants is also explained in Sections 5.0, 9.0 under subheading 9.2, and 15.0 of this protocol.

Visit 1:

Informed permission/assent/consent (PAC) from adult participant or child and parent/LAR will be obtained prior to study procedures being performed. All required elements of PAC will be documented in REDCap as this study will not be in the medical record per CM policy.

The study team will conduct a medical chart review to collect demographic information including date of birth, age, gender, height, weight, race, ethnicity, medical history, date of T1D diagnosis, treatment regimen, T1D-related hospitalizations, number of contacts and visits with clinic staff.

HbA1c is a proxy measure of glycemic control over the past 12 weeks. HbA1c will be collected from medical record via POC measures collected during routine diabetes clinic visits.

Glucometer, CGM, and/or pump uploads from SOC visits may be included to assess frequency of blood glucose checks or insulin delivery as a proxy measure of self-management adherence. We may also calculate mean daily blood glucose, percent high BG, percent low BG, and percent in range for glucose levels²¹, and insulin BOLUS scores²² from participants' device uploads.

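### Section 24.3 ends all data collection at study withdrawal, including the routine chart HbA1c, and does not say how to treat a participant who only stops the NUDGE texts

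*Combined protocol and SAP*

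**What the plan says.** Section 24.3 gives two rules. After withdrawal, "Study staff will not collect any study-related data on participants after their withdrawal from the study". Before it, "Data collected up to withdrawal will be included in the analyses", except for people withdrawn as ineligible. The template prompt for 24.3 also asks about "partial withdrawal from procedures with continued data collection", and the answer does not take this up.

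Section 9.2 tells participants that "they can refuse to participate in any component of the study protocol", and names withdrawal from the study as a further right in the same sentence. Section 24.1 adds: "The only foreseeable circumstances of withdrawal from the research without their consent would be subjects not meeting eligibility criteria".

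On outcomes, section 10.1 says that "HbA1c will be collected from medical record via POC measures collected during routine diabetes clinic visits", and section 25.1 places the values at baseline and about three months later. MVPA is measured in three wear weeks, starting at Days 1, 30 and 90 (section 5.3). Section 27.1 plans multilevel analyses of both outcomes. It names no analysis set, missing-data assumption or sensitivity analysis.

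**The concern.** This is a single-arm study, so efficacy is change from baseline, and selective loss of later measurements enters the effect size directly. People who leave may well be those whose activity did not rise. If their later values are missing, the MVPA and HbA1c effects lean towards people who stayed. Hypothesis 2 is judged against a medium effect, and section 27 says the pilot exists to supply power calculations for a larger study, so an inflated effect would make that study too small.

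Two features of 24.3 add to the loss without need. The chart HbA1c is given up at withdrawal although it requires no visit, device or survey for the study, and nobody is asked whether it may still be read. Also, no text says how to classify a participant who wants to stop the texts but would still wear the devices. Two staff members could treat that request differently, and one of the two readings ends follow-up.

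**Working it through.** **1. What triggers the rule**

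| Event | Section that speaks to it | Consequence for data |
|---|---|---|
| Participant refuses one component, such as the texts | 9.2 | Not stated; the person remains enrolled |
| Participant withdraws from the study | 24.3 | All collection stops; earlier data are analysed |
| Staff withdraw an ineligible participant | 24.1, 24.3 | Data excluded from the analyses |
| Participant leaves active procedures but would allow chart access | None (prompted in 24.3, unanswered) | The 24.3 stop applies by default |

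The first row has no stated data rule, and the fourth has no status of its own.

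**2. How much loss the plan allows for**

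Section 8.1 gives 50 evaluable and 70 consented. No loss rate is stated, so the 70 cannot be rebuilt independently. It can only be solved backwards: 50/(1 − x) = 70 gives x = 20/70 = 28.6%. The form defines this allowance as screen failures plus withdrawals and dropouts, so 28.6% is an upper bound on withdrawal.

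**3. Illustrative dilution**

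Assumptions not in the documents: d = 0.50 in stayers, change SD of 1 within each group, and medium taken as 0.5. The effect over everyone is (1 − loss) × 0.50 + loss × d in leavers.

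| Loss | Leavers d = 0 | Leavers d = 0.2 |
|---|---|---|
| 10% | 0.45 | 0.47 |
| 20% | 0.40 | 0.44 |
| 28.6% | 0.36 | 0.41 |

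Mixing two groups raises the SD slightly. At 28.6% loss with d = 0 in leavers, the SD is √(1 + 0.25 × 5/7 × 2/7) = 1.025, and 0.357/1.025 = 0.35.

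Required sample size goes with 1/d². Planning on 0.50 when the value over everyone is 0.45, 0.40 or 0.35 gives (0.45/0.50)² = 0.81, (0.40/0.50)² = 0.64 or (0.35/0.50)² = 0.49 of the size needed.

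**4. What the multilevel model recovers for MVPA**

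A random-intercept model was simulated with 70 participants, 20 leavers, three waves, within-person correlation 0.5 and 300 runs. Stayers gained 0.50 and leavers gained 0.

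| Leavers' data kept | Effect with everyone measured | Mixed model | Stayers only |
|---|---|---|---|
| Baseline only | 0.35 | 0.50 | 0.50 |
| Baseline and Day 30 | 0.35 | 0.45 | 0.49 |

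Keeping Day 30 moves the estimate part of the way back. With baseline only, the model recovers nothing here.

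**5. HbA1c**

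With two planned values there is no intermediate wave to help. Someone who withdraws before the second contributes no within-person change. For example, an assumed mean change of −0.30 points in stayers and 0 in leavers gives −0.30 × 50/70 = −0.21 over everyone at the upper bound.

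**The case against.** A reader might infer that anyone who quits NUDGE loses the Day 90 measurements. The text does not say so. The rule in 24.3 is triggered by withdrawal from the study, and 9.2 keeps refusal of a component separate from it. Staff-initiated withdrawal is foreseen only for ineligibility. Low response to the texts is an outcome in its own right, since Hypothesis 1 judges "feasibility based on ≥50% of daily text messages exchanged between youth and the intervention bot". Section 18.1 pays for wear, surveys and device return separately. This part of the objection stands: what remains is an unlinked pair of sections and a risk of inconsistent handling.

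A reader might also infer that efficacy is estimated only in those who stay. For MVPA that is too strong, because data up to withdrawal are analysed. It is close to true for HbA1c change and for MVPA in people who leave before Day 30.

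A third tempting step is to say that a medium effect would be overturned. That requires stayers to sit exactly at an assumed 0.50, leavers to show no effect, and all 20 of the 70 to be withdrawals whose data could have been recovered. The documents give no numeric cut-off and no withdrawal rate. With d = 0.63, the earlier two-group trial's figure in section 3.3, in stayers, 10% loss and no effect in leavers, the result is 0.63 × 0.9 = 0.57, or about 0.56 after the SD adjustment, which is still above 0.5.

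Finally, ending all collection when a family withdraws is a defensible privacy choice, and a pre-post effect in a single-arm pilot is not causal in any case. Both are true. Neither is a reason not to ask the participant, and full withdrawal stays available under the change proposed. The information letter is not in the reviewed documents and may already offer such a choice.

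**Conclusion.** The point holds as a gap that is cheap to close. Section 24.3 ends collection of even the routine chart HbA1c at study withdrawal, does not answer its own prompt on partial withdrawal, and is not tied to 9.2. The effect is most certain for HbA1c: withdrawal before the second value means no change score. For MVPA, retained data and the multilevel model reduce the selection without necessarily removing it.

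The size is unknown. Loss to withdrawal is at most 29% on the plan's own numbers and may be well below that. The dilution from 0.50 to about 0.45, 0.40 or 0.35 at 10%, 20% or 29% loss rests on assumed effects in stayers and leavers. It shows a direction and a plausible range, and does not predict the result.

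**What to change.** Rewrite 24.3 as follows.

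1. State that stopping or declining the NUDGE texts is not withdrawal from the study. Record the date, keep offering the Day 30 and Day 90 wear weeks and surveys, and keep taking the chart HbA1c and device data.
2. At full withdrawal, ask whether routine HbA1c and CGM data may still be taken from the record. Apply the rule against further data only if the answer is no.
3. Align the information letter if it does not already say this, and include both groups in the MVPA and HbA1c analyses.

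Naming a missing-data assumption and one sensitivity analysis in 27.1 would complete the change.

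The cost is one paragraph, possibly a sentence in the letter, one REDCap field for date and type of stopping, a few more device shipments and an IRB amendment. The gain is limited to participants willing to continue or to allow chart access. Those who refuse, stop responding or do not wear the devices are lost under any wording.
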